2. STATISTICAL ANALYSIS PLAN AUTHORSHIP

This SAP has been authored by [name], Trial Statistician for the EXPO study, (Senior statistician NWORTH CTU) with input from CI, [name], Co-lead Investigator, [name], [name] and [name]. [name], EXPO Trial Manager and [name], Senior Trial Statistician for the trial (Principal Statistician NWORTH CTU).

[name] (ZH Senior Trial Statistician) will remain blind throughout the conduct of the trial until the main analysis has been completed. [name] (RE) will be unblind for the purposes of reporting to the DMC. The draft plan has been circulated to the DMC members and TSC members for input and review prior to sign-off.

Statistician Blinding

Upon review of the protocol, it was noted that group numbers have been listed since protocol version 1.1. The Senior Statistician had reviewed and approved these protocols and the use of these group numbers could potentially unblind them to the treatment groups. These codes appear to be unblind with group 1 and 2 relating to phase 1 and groups 3 and 4 relating to phase 2.

It has not been confirmed either way which group these relate to explicitly however to ensure that the Senior Statistician remains blind to the data for analysis, the Trial Statistician will re-label the groups prior to analysis. The data using this relabelling will be used by the Senior Statistician to ensure blinding is maintained. All work will follow a full audit trail and documented in line with NWORTHs SOPs and MHRA guidance.

3. INTRODUCTION

3.1 BACKGROUND AND DESIGN

Background

Daily doses of sublingual (tablet) buprenorphine hydrochloride (BUP-SL) and oral (liquid) METadone hydrochloride (MET) are the first-line, standard-of-care (SOC) maintenance pharmacotherapies for OUD. MET is an opioid agonist with actions predominantly at the endogenous μ -opioid receptor. BUP is an opioid partial agonist/antagonist with actions predominantly at the endogenous μ -opioid and κ (kappa) opioid receptors. In the UK, two other licensed BUP medications are also available for OUD – buprenorphine-naloxone (buprenorphine hydrochloride-naloxone dihydrate; Suboxone®; sublingual tablet; BUP-NX)

and buprenorphine-lyophilisate; ESPranor®; sublingual wafer; ESP). BUP-NX contains the opioid antagonist naloxone (1:4 ratio with BUP) as a deterrent to injection of non-medical opioids. Indivior developed a subcutaneously injected, extended-release formulation of BUP (RBP6000). RBP6000 releases BUP for a minimum of 28 days, thereby facilitating monthly maintenance dosing. RBP6000 is now licensed as Sublocade® in the USA (BUP-XR herein).

Design

The EXPO study will determine the effectiveness of BUP-XR in a head-to-head superiority comparison with BUP-SL/MET (phase 1) and with an adjunctive psychosocial intervention (PSI) (phase 2) in the pragmatic context of specialist community setting addiction treatment programmes in England and Scotland provided by the NHS.

The Trial is a Phase III (CTIMP; IMP open-label, oral IMP comparators [no placebo]), multi-centre, pragmatic, two-phase, randomised controlled trial. With a target total sample of 604 patients with Opioid Use Disorder (OUD; moderate-severe; DSM5), participants are allocated to one of four trial arms:

- BUP-XR
- BUP-SL/MET (including BUP-SL-NX and ESP)
- BUP-XR + PSI
- BUP-SL/MET (including BUP-SL-NX and ESP) + PSI

As BUP is the active component of BUP-SL-NX and ESP they will be categorised under BUP-SL within the remainder of this SAP and for analysis between trial arms.

Treatments

BUP extended-release depot injection (USA Sublocade®; BUP-XR) is administered by subcutaneous injection into abdominal tissue. BUP-XR is available as a 100mg/0.5ml and 300mg/1.5ml pre-filled syringe. In EXPO, the drug is administered as two initial doses of 300mg given a minimum of 21 days apart, followed by 4 x 100 mg monthly maintenance doses.

Within the regimen and if the benefits are judged to outweigh the risks: (1) The 100 mg maintenance dose may be increased and maintained to 300mg if there is unsatisfactory clinical response (i.e. dose 3-6); (2) A 300 mg maintenance dose (i.e. dose 4 and 5) may be

reduced to 100 mg according to clinical assessment; (3) BUP-SL (including BUP-SL-NX and ESP) will be given on a rescue basis for patients who do not achieve a satisfactory clinical response to BUP-XR.

Active comparator product(s);

- (1) BUP-SL (sublingual [tablet] BUP-SL), or substitute 4:1 ratio BUP-SL/naloxone 'Suboxone' [BUP-SL-NX] usual dose 12-24mg/day; or substitute oral lyophilisate ESPranor (ESP) usual dose 9-18mg/day) are longstanding standard-of-care maintenance pharmacotherapy for OUD in the NHS;
- (2) MET (oral methadone hydrochloride; usual dose 60-120mg/d), longstanding standard-of-care maintenance pharmacotherapy for OUD in the NHS.

Trial Phases

The study consists of two phases. Phase 1 of the study refers to the analysis of BUP-XR and BUP-SL/MET and phase 2 refers to the analysis of BUP-XR + PSI and BUP-SL/MET + PSI. There will be separate statistical analysis plans for the two study phases. Recruitment in phase 1 of the study is on a 1:1 allocation ratio to BUP-XR and BUP-SL/MET across 4 clinical recruitment sites in the West Midlands, Greater Manchester, Newcastle and Tayside. During phase 1, the South London site will recruit to groups on a 4:4:1:1 allocation ratio for approximately 6 months whilst resources are in place to allow more participants to be allocated to psychosocial therapy (e.g. therapists in post). During the subsequent approximate 18 months of recruitment, there will be a 1:1 allocation ratio to BUP-XR + PSI and MET/BUP-SL + PSI (only at the South London site). The timescales for these ratios may change depending on recruitment levels and resource availability. Figure 1 below represents the study's randomisation structure across sites. The current statistical analysis plan (SAP) only concerns phase 1 of the study.

[figure not shown]

Figure 1: Randomisation summary for Phase 1 and Phase 2 of EXPO study

Analysis set

Primary analysis will be conducted on an intention to treat (ITT) basis, defined as all participants that are randomised are analysed as allocated, regardless of their treatment.

Certain circumstances may occur that result in randomised participants not being analysed. Such circumstances can arise if patients are randomised in error, e.g.

- If the same participant is mistakenly randomised twice
- If an ineligible patient is randomised and must be withdrawn from the study Eligibility violations

If any post randomisation eligibility violations are identified, the study team along with the sponsor and independent committees will establish whether the participant can remain in the study. For cases where the criteria violated does not affect clinical outcome or patient safety these participants will be kept in the ITT analysis set. Sensitivity analysis will be conducted

removing eligibility violations by conducting a modified intention to treat (mITT) analysis, see section 6.9 for more details.

All exclusions due to randomisation errors or eligibility violations will be reported clearly.

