Group 4: Bup/Met + PSI (Total from Phase I and Phase II 150 South London site only)

The senior statistician will be blinded. The junior statistician is unblinded so that reports can be prepared. Research and clinical team will also be unblinded.

*Due to the Coronavirus 2019 (COVID-19) pandemic and slower than anticipated recruitment rate, recruitment into Phase I and Phase II will be completed at the same time; target quarter 4 2021.

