6.9 SENSITIVITY ANALYSES OR MODEL TESTING

Sensitivity analysis will be conducted on the primary analysis model including the variables that were identified as predictors of missingness as covariates in the model.

Additionally, sensitivity analysis may be required around any assumptions made for the primary analysis (e.g. outliers, data distributions) but will only be conducted if necessary. This will include a best-case worst-case analysis on the self-report missing data on the primary outcome. Best case would assume that patients did not use during any missing time periods and worst case would assume that they did use substances to evaluate any impact the imputed data may have had on the results.

Furthermore, the confidence of the reliability of the self-report will be checked by conducting a best-case worst-case sensitivity analysis on the UDS missing data for the TLFB outcomes.

For those who have a missing UDS, we will assume all missing as negative for one dataset and then for another dataset assume all missing as positive. Utilising this best –worst case scenario will provide a range of values between which the real outcome is likely to lie. The width of this range is likely to be influenced by many factors (including the COVID pandemic and not being able to collect the UDS).

Primary and secondary analysis will be conducted on an ITT basis (including all those randomised to be analysed. Sensitivity analysis may be conducted, if necessary, on protocol deviations or eligibility violations by removing them from the analysis set. This includes protocol deviations (but is not limited to) such as;

- Patients not receiving randomized allocation (per protocol analysis)
- Patients not receiving treatment within 7 days (per protocol analysis)
- Ineligible patients being randomised (mITT analysis)

Sensitivity analysis will be conducted on the patient's months in treatment (for current episode) at baseline by running the model including the variable as a factor.

Additionally, sensitivity analysis of the patient's preference of BUP-SL or MET will be conducted again by running the model including that variable as a factor. This will be conducted given that there is an adequate sample of data per group at each level of the variable (BUP-SL or MET) a sample of 50% – 60% in the MET group will indicate that we will run this sensitivity analysis.

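### SAP 3.1 allows some ineligible randomised participants to leave the primary ITT set on a post-randomisation judgement with no blinding condition, in conflict with SAP 6.9 and Protocol 12.2

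*SAP*

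**What the plan says.** SAP 3.1, under Analysis set, opens with the usual definition: "Primary analysis will be conducted on an intention to treat (ITT) basis, defined as all participants that are randomised are analysed as allocated". It then qualifies it: "Certain circumstances may occur that result in randomised participants not being analysed". Two examples follow. One is a participant randomised twice; the other reads "If an ineligible patient is randomised and must be withdrawn from the study".

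For violations found after randomisation, SAP 3.1 says that "the study team along with the sponsor and independent committees will establish whether the participant can remain in the study". It then gives the retention rule: "For cases where the criteria violated does not affect clinical outcome or patient safety these participants will be kept in the ITT analysis set". A modified ITT (mITT) sensitivity analysis without eligibility violations is planned, and all such exclusions are to be reported.

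Two other sections describe the primary set without exceptions. Protocol 12.2 counts every patient in the arm assigned. SAP 6.9 takes in everyone randomised and places ineligible participants under mITT. On blinding, Protocol 5.2 states: "Research and clinical team will also be unblinded". Of the two statisticians, only the senior one is blinded.

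**The concern.** The primary set has two definitions. Under Protocol 12.2 and SAP 6.9 an ineligible participant is analysed as allocated. Under SAP 3.1 the same participant may not be analysed if withdrawn as ineligible or, by the converse of the retention rule, if the breached criterion is judged relevant to outcome or safety.

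The SAP 3.1 route matters because the judgement comes after randomisation in an open-label trial. The SAP does not require it to be made blind to arm and outcome, to rest only on pre-randomisation information, or to be made before outcome data accrue. If exclusions fell unevenly across arms and the people excluded had a different prognosis, the comparison of days abstinent would be biased. No planned analysis would reveal this, because mITT removes further participants and nothing puts the excluded ones back.

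Uneven exclusion is plausible. Inclusion criterion 3 (Protocol 8.1) asks whether the clinician thinks the patient could convert to XR-Bup within 7 days of randomisation, and only the XR-Bup arm then attempts the conversion.

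**Working it through.** **The rules side by side**

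| Situation | SAP 3.1 | SAP 6.9 | Protocol |
|---|---|---|---|
| Violation judged irrelevant to outcome and safety | Kept in ITT | In ITT | In ITT (12.2) |
| Violation judged relevant to outcome or safety | Out, by implication | In ITT; removed only in mITT | In ITT (12.2) |
| Ineligible and withdrawn from the study | May go unanalysed | In ITT; removed only in mITT | In ITT (12.2) |
| XR-Bup conversion declined or judged unsuitable | Not addressed as such | Non-receipt of allocation is a per-protocol sensitivity matter | Withdrawn, but labelled ITT population (8.3) |

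The second and third rows conflict. The fourth leaves a boundary case: the documents do not say which rule governs if a failed conversion is reclassified as a breach of criterion 3.

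**Possible size (illustration)**

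The plan gives no figure for violators, their outcomes or the standard deviation (SD) of the endpoint, so there is no plan figure to reproduce.

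*From the documents (SAP 4.1):* control rate 0.6, a 23% target difference (read as relative), 161 days, 304 participants, so 152 per arm.

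- Control mean: 0.6 × 161 = 96.6 days.
- Target mean: 96.6 × 1.23 = 118.8 days.
- Target difference: 118.8 − 96.6 = 22.2 days.

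*Assumed:* k participants are excluded from one arm only, and their mean count is D days below the whole-arm mean, with D from 40 to 60. The arm mean then rises by k × D / (152 − k).

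For type I error, assume also a common SD S of 40 to 60 days, no true effect and a normal approximation. The shift in the test statistic is δ = shift / [S × √(1/(152 − k) + 1/152)], and the two-sided rejection probability is 1 − Φ(1.96 − δ) + Φ(−1.96 − δ).

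Example with k = 8, D = 40, S = 40: shift = 320/144 = 2.22 days; δ = 2.22/(40 × 0.1163) = 0.48; rejection probability 7.7%.

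| Excluded from one arm | Shift, D = 40 | Shift, D = 60 | Share of 22.2 days | Type I error, S = 40 to 60 |
|---|---|---|---|---|
| 3 | 0.8 | 1.2 | 4–5% | 5.2–5.8% |
| 5 | 1.4 | 2.0 | 6–9% | 5.4–7.3% |
| 8 | 2.2 | 3.3 | 10–15% | 6.2–11.1% |
| 15 | 4.4 | 6.6 | 20–30% | 9.5–28.6% |

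If similar numbers with the same D left both arms, both means would rise together and the shifts would largely cancel. With everyone retained, k = 0 and this source of bias is zero. The target of 304 does not change.

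**The case against.** The strongest reply is that SAP 3.1 never says in terms that the remaining violators are dropped; it says only who is kept. Protocol 12.2 and SAP 6.9 include everyone, an mITT analysis needs violators in the primary set to remove, and every exclusion will be reported. Independent committees share the decision, and Protocol 8.4 has eligibility confirmed before randomisation in both arms.

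Part of this stands. Removal under the retention rule is an inference. It is a fair one, because the same section says that randomised participants may go unanalysed, names the withdrawn ineligible patient as an example and provides for reporting exclusions. The mITT analysis does not settle the matter: it would still have the retained violators to remove. Reporting makes exclusions visible but does not undo them.

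A reader might also infer more than the documents support:

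- *That an unblinded team decides alone.* It decides with the sponsor and independent committees. The gap is the lack of any blinding or data condition on that joint decision.
- *That participants are removed because of how they did.* The test concerns the type of criterion breached, not the participant's observed days abstinent.
- *That every XR-Bup patient has eligibility reassessed before injection, so violations surface mainly there.* Protocol 8.3 describes converting medication, not a second eligibility review, and places failed conversions in the ITT population. On-treatment liver tests are required by protocol only in the XR-Bup arm, but a later abnormal result is not in itself an entry violation.
- *That the randomised comparison is broken.* The documents allow a biasing exclusion; they do not show one.

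**Conclusion.** The point holds as a conflict in the definition of the primary analysis set, one side of which permits avoidable post-randomisation exclusions. SAP 3.1 is wrong as written because it departs from its own definition, from SAP 6.9 and from Protocol 12.2, and sets no condition that would protect the judgement from knowledge of arm or outcome.

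Whether bias would follow depends on how many are excluded, how unevenly, and how their outcomes differ; the documents give none of these. Under the assumed one-arm scenarios with 5 to 15 exclusions, the arm mean shifts by 1.4 to 6.6 days, or 6 to 30% of the 22.2-day target. With three or fewer excluded, type I error stays between 5 and 6%. The direction depends on which arm loses participants and on whether they would have done worse or better than average. This should be corrected before database lock, but it is not by itself a reason to doubt the trial.

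**What to change.** Reword SAP 3.1 so that:

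1. Every randomised participant stays in the primary ITT set as allocated, including those withdrawn from treatment as ineligible, using the data available. A duplicate randomisation is counted once, at the first.
2. Eligibility exclusions apply only in the mITT sensitivity analysis. SAP 3.1 says that analysis will be done and SAP 6.9 says it may be; make it definite in both.
3. Failed XR-Bup conversions stay in the primary set however they are classified, consistent with Protocol 8.3.
4. SAP 3.1, SAP 6.9 and Protocol 12.2 describe the same set.

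If any primary exclusion is kept, require that it be decided blind to arm and outcome, from pre-randomisation information only and by the same rule in both arms, and add a sensitivity analysis that restores those excluded.

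Protocol 8.5 already asks withdrawing participants for the time-line follow-back and urine screen data, so this needs no new procedure. A participant with no data from day 8 on has no exposure for the SAP 4.6 offset, so report the number of these by arm.

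The cost is SAP wording. A few ineligible patients stay in the primary analysis, which may slightly dilute the effect; the mITT analysis will show by how much. Decisions on withdrawing anyone from treatment for safety are unaffected.

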3.2 TRIAL OBJECTIVES

Primary Objective:

During six months of active trial treatment, the primary objective of this superiority study is to determine the difference in effectiveness (in terms of reduced use of heroin and illicit opioids) of BUP-XR and either MET or BUP-SL. Study participation will be offered to patients already enrolled in BUP-SL and MET maintenance treatment.

With a 1-week measurement grace period from randomisation, the primary endpoint is the count of days abstinent from heroin and illicit opioids during six months of treatment combined with urine drug screen samples which are negative for non-medical opioids.

Secondary Objectives:

To explore study group differences on the following measures:

[figure not shown]
- (1) *Clinical superiority of BUP-XR plus PSI versus BUP-SL/MET plus PSI;
- (2) Safety of BUP-XR;
- (3) Treatment retention;
- (4) OUD and CUD remission status;
- (5) Clinician rated impression of patient response to treatment;
- (6) Patient reported recovery outcomes;
- (7) Mediation of craving, depression, work and social adjustment, and cognitive function on outcome.

* Secondary Objective (1) not covered by this SAP as is part of phase 2 analysis.

Additionally, longer-term outcomes will be collected through data-registry indicators of criminal convictions and health service utilisation. The analysis of these outcomes are not included in this SAP.

3.3 CONSORT DIAGRAM

CONSORT 2010 Flow Diagram

4. STATISTICAL PRINCIPLES

4.1 SAMPLE SIZE JUSTIFICATION

The required number of participants has been estimated using that required for a Poisson regression model taking a baseline rate of 0.6 (60% abstinent days per month) and assuming a 23% target difference in the count of days of abstinence from heroin over the study period of 161 days. This target difference is informed by results of the ARC trial (ISRCTN69313751): 56.78% for the treatment-as-usual control (i.e. assuming 17 abstinent days over a period of 28 days).

To obtain 90% power, for a Poisson regression, with alpha at 5% and with 15% inflation for attrition, EXPO has a target total of 304 participants for the statistical comparison of the primary outcome recorded for BUP-XR and MET/BUP-SL.

A sensitivity check on the power calculation on the assumption of a greater response has been completed. With a sample of 304 subjects and a 23% target difference achieved, a higher baseline rate of 0.75 observed would achieve 97.5% statistical power.

Additionally, a sensitivity check has been conducted assuming a reduced baseline rate. With a sample of 304 subjects and a 23% target difference achieved, a baseline rate of 0.5 observed would achieve 88% statistical power.

A power analysis will be completed as part of the main analysis for the study.

4.2 RANDOMISATION

Online randomisation system will be provided by King's CTU. Randomisation procedure will be on a 1:1 allocation ratio by stratified block with random varying block sizes, stratified for Centre (West Midlands, Manchester, Newcastle and Tayside) and Current (last 28 days) drug injecting status (yes/no). At South London for approximately the first 6 months (subject to change depending on resource and recruitment rates) of recruitment, patients will be randomised to one of four groups on a 4:4:1:1 allocation ratio, with Current (last 28 days) drug injecting status (yes/no). Figure 1 in section 3.1 portrays this.

Justification for these stratification factors is as follows: (a) site is required for the random-effects model; (b) it is expected that there will be relatively poorer outcome among participants who are drug injectors. The randomisation procedure will use stratified random blocks of varying size to ensure even allocation.

4.3 LEVELS OF CONFIDENCE AND P-VALUES

All statistical tests for the primary endpoints will be two-sided and will be performed using a 5% significance level. Confidence intervals for estimated effects will be presented as 95% and two-sided.

Secondary outcomes will not be adjusted for multiple comparisons, as standard. The primary outcome is powered for at the significance level stated. Analysis of all secondary outcomes is considered exploratory, and any statements of results related to these outcomes will be reported appropriately. 95% confidence intervals will be reported along with the p-value of the effect.

4.4 ADHERENCE

BUP-SL (including BUP-SL-NX and ESP) (active sublingual comparator): The usual dose is 12-24mg/day (ESP usual dose 8-18mg/day). Clinical practice in NHS clinics is supervised (directly observed dosing) in a community pharmacy followed by provision of patient self-administered 'take home' doses according to clinical response (i.e. informed by negative urine drug screens [UDS]; adherence to prescription; retention in treatment).

MET (active oral comparator): The usual dose is 60-120mg/day. Clinical practice in NHS clinics is supervised (directly observed dosing) in a community pharmacy followed by provision of patient self-administered 'take home' doses according to clinical response (i.e. informed by negative UDS; adherence to prescription; retention in treatment).

Adherence to the intervention will be reported descriptively using the BUP-XR Injection Log and for the comparator the BUP-SL/MET Medication Record form and UDS. This will include injection frequencies, patterns of dosage (i.e. injection size in mg), oral medication frequencies and patterns of dosages.

